#### **Missing Data Imputation for Virologic Failure**

If HCV RNA values from the central laboratory are missing but a local laboratory value is present in the appropriate time period, then the local laboratory value will be used to assess post-treatment relapse and on-treatment virologic failure.

#### Missing Data Imputation for PRO Questionnaires

The handling of missing data for PROs will be as follows. For EuroQol-5 Dimensions-5 Level (EQ-5D-5L) index and VAS scores, no imputation will be performed for missing items. The missing items of the Fatigue Severity Scale (FSS) questionnaire will be imputed with the average score of the answered items as long as more than 50% of the items on the FSS are answered.

## 9.3 Primary Efficacy Endpoint and Analyses

## 9.3.1 Primary Efficacy Endpoint

The primary efficacy endpoint is the achievement of  $SVR_{12}$  (defined as HCV RNA < LLOQ 12 weeks after the last actual dose of study treatment) for each subject in the ITT population.

### 9.3.2 Main Analysis of Primary Efficacy Endpoint

The attributes of the estimand corresponding to the primary efficacy endpoint are summarized in Table 2.

## Table 2.Summary of the Estimand Attributes Corresponding to the
Primary Efficacy Endpoint

	Attributes of the Estimand				
Estimand Label	Treatment	Endpoint	Population	Handling of Intercurrent Events	Statistical Summary
Primary	GLE/PIB 8 Weeks	SVR 12	ITT	Subjects who discontinue the study with an unknown SVR 12 status (after applying backward imputation) will be counted as a failure for SVR 12	Number and percentage of subjects who achieve SVR 12 along with a two-sided 95% CI calculated using Wilson's score method 

The superiority of 8-week treatment with GLE/PIB in acute HCV infection to the weighted efficacy threshold described in Section 2.5, which is based on the historical ITT SVR12 rate of treatment with GLE/PIB in PWID and non-PWID subjects with chronic HCV infection, will be demonstrated if the lower bound of the two-sided 95% CI for the percentage of subjects achieving SVR12 is greater than the weighted efficacy threshold. For the calculation of the efficacy threshold, the proportions of PWID and non-PWID subjects in this study will be determined using PWID Status Classification 1 described in Section 7.1.

The number and percentage of subjects with each reason for  $SVR_{12}$  non-response will be provided. A listing of subjects who do not achieve  $SVR_{12}$  by reason for non-response will also be provided.

### 9.3.3 Supplementary Analyses of Primary Efficacy Endpoint

As a supplementary analysis of the primary endpoint (Supplementary Analysis 1), the number and percentage of subjects in the ITT population who achieve SVR12 along with a two-sided 95% CI calculated using Wilson's score method will be compared to the

efficacy threshold as calculated using the proportions of PWID and non-PWID subjects in this study and the PWID Status Classifications 2 and 3 as described in Section 7.1.

As a supplementary analysis of the primary endpoint (Supplementary Analysis 2), the number and percentage of subjects in the ITT population with baseline HCV RNA  $\geq$  LLOQ who achieve SVR12 along with a two-sided 95% CI calculated using Wilson's score method will be compared to the efficacy threshold as calculated using the proportions of PWID and non-PWID subjects included in this analysis and the PWID Status Classifications 1, 2, and 3 as described in Section 7.1. Additionally, the number and percentage of subjects with each reason for SVR12 non-response will be provided as well as a listing of subjects who do not achieve SVR12 by reason for non-response.

## 9.4 Secondary Efficacy Endpoints and Analyses

## 9.4.1 Key Secondary Efficacy Endpoint

The key secondary efficacy endpoint is the achievement of  $SVR_{12}$  for each subject in the mITT-VF population.

## 9.4.2 Main Analysis of Key Secondary Efficacy Endpoint

The attributes of the estimand corresponding to the key secondary efficacy endpoint are summarized in Table 3.

## Table 3.Summary of the Estimand Attributes Corresponding to the Key
Secondary Efficacy Endpoint

			Attributes of	the Estimand	
Estimand Label	Treatment	Endpoint	Population	Handling of Intercurrent Events	Statistical Summary
Key Secondary	GLE/PIB 8 Weeks	SVR 12	mITT-VF	Not applicable	Number and percentage of subjects who achieve SVR 12 along with a two-sided 95% CI calculated using Wilson's score method 

The superiority of 8-week treatment with GLE/PIB in acute HCV infection to the weighted efficacy threshold described in Section 2.5, which is based on the historical mITT-VF SVR12 rate of treatment with GLE/PIB for PWID and non-PWID subjects with chronic HCV infection, will be demonstrated if the lower bound of the two-sided 95% CI for the percentage of subjects achieving SVR12 is greater than the efficacy threshold. The key secondary hypothesis will be tested only if the primary efficacy hypothesis is demonstrated according to the fixed-sequence testing procedure described in Section 12.0. For the calculation of the efficacy threshold, the proportions of PWID and non-PWID subjects in this study will be determined using PWID Status Classification 1 described in Section 7.1.

The number and percentage of subjects with each reason for  $SVR_{12}$  non-response will be provided.

### 9.4.3 Supplementary Analyses of Key Secondary Efficacy Endpoint

As a supplementary analysis of the key secondary endpoint, the number and percentage of subjects in the mITT-VF population who achieve  $SVR_{12}$  along with a two-sided 95% CI calculated using Wilson's score method will be compared to the efficacy threshold as

calculated using the proportions of PWID and non-PWID subjects in this study and the PWID Status Classifications 2 and 3 as described in Section 7.1.

As a supplementary analysis of the key secondary endpoint, the number and percentage of subjects in the mITT-VF population with baseline HCV RNA  $\geq$  LLOQ who achieve SVR12 along with a two-sided 95% CI calculated using Wilson's score method will be compared to the efficacy threshold as calculated using the proportions of PWID and non-PWID subjects included in this analysis and the PWID Status Classifications 1, 2, and 3 as described in Section 7.1. Additionally, the number and percentage of subjects with each reason for SVR12 non-response will be provided.

## 9.4.4 Supportive Secondary Efficacy Endpoints and Analyses

The supportive secondary efficacy endpoints are:

- On-treatment virologic failure (as defined in Section 9.1) for each subject in the ITT population;
- Relapse12 (as defined in Section 9.1) for each subject in the ITT population who completed treatment as planned (defined as study treatment duration ≥ 52 days) with HCV RNA < LLOQ at EOT and with at least 1 post-treatment HCV RNA value;

- Post-treatment reinfection with HCV (as defined in Section 9.1) for each subject in the ITT population.

For the analysis of on-treatment virologic failure, Relapse12, and post-treatment HCV reinfection, the number and percentage of subjects in the ITT population will be summarized along with a two-sided 95% CI calculated using Wilson's score method.

Subject numbers of all virologic failures and subjects with post-treatment reinfection will be provided.

## 9.5 Additional Efficacy Analyses

The following additional efficacy endpoints will be summarized for the ITT population:

- At each post-baseline visit in the Treatment Period, achievement of HCV RNA < LLOQ (using data as observed);
- Achievement of SVR4 (as defined in Section 9.1);
- Virologic failure through Post-Treatment Week 12 (as defined in Section 9.1);
- Relapseoverall (as defined in Section 9.1).

For each of the endpoints above, the number and percentage of subjects meeting the endpoint will be calculated. For the endpoints of SVR4 and virologic failure, a two-sided 95% CI will be calculated using Wilson's score method. Imputations for missing data will be performed as described in Section 9.2 for analysis of SVR4, where a missing response will be imputed as a failure after performing the described imputation. All other endpoints will be presented using data as observed.

A summary of the subjects in the ITT population who completed treatment and relapsed (defined as **Relapse**overall) will be prepared displaying the number of subjects relapsing overall and by SVR visit window (within the SVR4 or SVR12 window or after SVR12 window), including the subject number and the SVR visit window corresponding to the first HCV RNA value of those indicating the occurrence of relapse. A similar summary will be prepared for subjects in the ITT population who prematurely discontinued treatment and relapsed after having HCV RNA < LLOQ at their Final Treatment Visit.

A listing of subjects in the ITT population excluded from the relapse denominator (e.g., study treatment duration < 52 days or no post-treatment HCV RNA) will be provided, as applicable.

The concordance between  $SVR_4$  and  $SVR_{12}$  will be assessed for the ITT population by the agreement between  $SVR_4$  and  $SVR_{12}$  and the positive predictive value (PPV) and negative predictive value (NPV) of  $SVR_4$  on  $SVR_{12}$ . The agreement between  $SVR_4$  and  $SVR_{12}$  is a percentage defined as the number of subjects achieving both  $SVR_4$  and  $SVR_{12}$  and the

number of subjects where both  $SVR_4$  and  $SVR_{12}$  are not achieved. The PPV of  $SVR_4$  on  $SVR_{12}$  is the proportion of subjects who achieve  $SVR_{12}$  out of all subjects who achieved  $SVR_4$ . The NPV of  $SVR_4$  on  $SVR_{12}$  is the proportion of subjects who do not achieve  $SVR_{12}$  out of all subjects who did not achieve  $SVR_{12}$  out of all subjects who did not achieve  $SVR_4$ .

## 9.6 Efficacy Subgroup Analyses

The number and percentage of subjects achieving SVR12 in the ITT and mITT-VF populations will be presented for the following subgroups:

- HCV GT (1, 2, 3, 4, 5, or 6) and available subtype (final HCV genotype and subtype as defined in Section 9.7);
- Sex (male or female);
- Age (< 18, 18 to < 40, 40 to < 65, 65 to < 75, ≥ 75 years; < 18 or ≥ 18 years;

   < 65 or ≥ 65 years; < 75 or ≥ 75 years);

- Race (white, black/African-American, Asian, or other) and (black or non-black);
- BMI (< 30 or  $\ge$  30 kg/m^2);
- Baseline HCV RNA level (< 800,000 or ≥ 800,000 IU/mL; < 1,000,000 or ≥ 1,000,000 IU/mL);
- Baseline platelet count (< 100 or  $\geq$  100 × 10^9/L);
- Baseline serum albumin (< 35 or  $\geq$  35 g/L);
- Baseline ALT (≤ ULN, > ULN to ≤ 3 × ULN, > 3 × ULN to ≤ 5 × ULN, > 5 × ULN to ≤ 10 × ULN, or > 10 × ULN);
- Baseline total bilirubin (< 34.2 or  $\geq$  34.2  $\mu$ mol/L);
- Geographic region (North America, Europe, or ROW);
- Baseline creatinine clearance (<  $60, \ge 60$  to <  $90, \text{ or } \ge 90 \text{ mL/min}$ );
- Baseline eGFR (< 90 or  $\geq$  90 mL/min/1.73 m^2);
- History of diabetes (yes or no);

- History of opiate substitution therapy use (yes, ongoing at start of study treatment; yes, less than 6 months prior to start of study treatment; yes, 6 to 12 months prior to start of study treatment; yes, more than 12 months prior to start of study treatment; yes, timing of last dose unknown; or no);
- History (i.e., started prior to start of study treatment) of non-prescribed illicit drug use (yes, ongoing as of the end of study participation; yes, last dose after last dose of study treatment; yes, last dose during study treatment period; yes, last dose less than 6 months prior to start of study treatment; yes, last dose more than 12 months prior to start of study treatment; yes, last dose more than 12 months prior to start of study treatment; yes, last dose unknown; or no);
- History (i.e., started prior to start of study treatment) of non-prescribed illicit injection drug use (yes, ongoing as of the end of study participation; yes, last dose after last dose of study treatment; yes, last dose during study treatment period; yes, last dose less than 6 months prior to start of study treatment; yes, last dose 6 to 12 months prior to start of study treatment; yes, last dose more than 12 months prior to start of study treatment; yes, timing of last dose unknown; or no);
- PWID Status Classification 1 with respect to study treatment start (current/recent PWID or former/non-PWID; current PWID, recent PWID, former PWID, or non-PWID);
- PWID Status Classification 2 with respect to study treatment period (current/recent PWID or former/non-PWID; current PWID, recent PWID, former PWID, or non-PWID);
- PWID Status Classification 3 with respect to study participation (current/recent PWID or former/non-PWID; current PWID, recent PWID, former PWID, or non-PWID);
- Baseline APRI ( $\leq 1, > 1$  to  $\leq 2$ , or > 2);
- Baseline FibroTest (< 0.75 or  $\geq$  0.75);
- Baseline FIB-4 (< 1.45,  $\ge 1.45$  to  $\le 3.25$ , or > 3.25);
- Baseline AST/ALT ratio ( $\leq 1 \text{ or } > 1$ );

- Risk behavior for acute HCV infection (shared drug-injection equipment, shared non-injection drug use equipment, unprotected sexual activity with multiple partners, unprotected sexual activity with other male(s), risky tattoos or body piercings, shared personal items possibly contaminated with blood, healthcare worker with occupational exposure, or other behavior);
- Grouped risk behavior for acute HCV infection (contaminated needle or IV drug use, contact with infected individual, occupational exposure, or other behavior);
- Grouped risk behavior for acute HCV infection (drug use, sexual transmission, contact by contaminated objects, occupational, other behavior);
- Baseline HCV/HIV co-infection status (HCV mono-infected or HCV/HIV-1 co-infected);
- Estimated acute HCV infection duration (< 3 months, ≥ 3 months to

   < 6 months, or ≥ 6 months) across all and by each acute HCV infection criteria used to estimate infection duration;

- History of prior HCV infection (yes or no);
- Baseline fibrosis stage (equivalent to Metavir F0 F1, F2, F3, or F4);
- Baseline cirrhosis status (cirrhotic, non-cirrhotic, or unknown test results indeterminate);
- Treatment duration (< 52 days or  $\geq$  52 days);
- Study treatment compliance (yes or no).

The number and percentage of subjects with each reason for  $SVR_{12}$  non-response will be presented for the following subgroups:

- PWID Status Classification 1 with respect to study treatment start (current/recent PWID or former/non-PWID; current PWID, recent PWID, former PWID, or non-PWID);
- History of opiate substitution therapy use (yes, ongoing at start of study treatment; yes, less than 6 months prior to start of study treatment; yes, 6 to 12 months prior to start of study treatment; yes, more than 12 months prior to start of study treatment; yes, timing of last dose unknown; or no).

The number and percentage of subjects with on-treatment virologic failure, Relapse12, and post-treatment HCV reinfection in the ITT population will be presented for the following subgroups:

- Age (< 18, 18 to < 40, 40 to < 65, 65 to < 75, ≥ 75 years; < 18 or ≥ 18 years;

   < 65 or ≥ 65 years; < 75 or ≥ 75 years);

- PWID Status Classification 1 with respect to study treatment start (current/recent PWID or former/non-PWID; current PWID, recent PWID, former PWID, or non-PWID);
- PWID Status Classification 2 with respect to study treatment period (current/recent PWID or former/non-PWID; current PWID, recent PWID, former PWID, or non-PWID);
- PWID Status Classification 3 with respect to study participation (current/recent PWID or former/non-PWID; current PWID, recent PWID, former PWID, or non-PWID);
- Baseline HCV/HIV co-infection status (HCV mono-infected or HCV/HIV-1 co-infected).
- History of opiate substitution therapy use (yes, ongoing at start of study treatment; yes, less than 6 months prior to start of study treatment; yes, 6 to 12 months prior to start of study treatment; yes, more than 12 months prior to start of study treatment; yes, timing of last dose unknown; or no);

The two-sided 95% confidence interval using Wilson's score method will be produced if there are at least 5 subjects in the subgroup.

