5.4 Prior and Concomitant Therapy

Any medication or vaccine (including COVID-19 vaccines), over-the-counter or prescription medicines, vitamins, and/or herbal supplements that the subject is receiving at the time of enrollment or receives during the study must be recorded from at least 14 days prior to study drug administration through 14 days following discontinuation of study drug. After 14 days post-treatment, antiviral therapies related to the treatment of HCV, medications prescribed in association with an SAE, and opiate substitution therapy must be recorded. Nonprescribed illicit drug use must be recorded throughout the study.

Any questions regarding concomitant or prior therapy should be raised to the AbbVie Medical Director or Scientific Director. Information regarding potential drug interactions with GLE/PIB can be located in the GLE/PIB Investigator's Brochure.

COVID-19 Pandemic-Related Vaccination Guidance

Given the ongoing COVID-19 pandemic, selected non-live vaccines (e.g., messenger RNA, non-replicating viral vector, protein subunit, etc.) to prevent SARS-CoV-2 infection may be administered during screening or the treatment period, as long as the vaccine is not contraindicated or medically inappropriate.

The decision to receive a locally available vaccine should be based on local guidance and an individual discussion between the treating physician and the subject.

The potential impact of GLE/PIB on SARS-CoV-2 vaccination is unknown. Therefore, study drug should be administered as follows:

- The first dose of study drug GLE/PIB, when possible, is preferred to be given at least ± 7 days from any SARS-CoV-2 vaccine administration.
- GLE/PIB dosing should not be interrupted due to SARS-CoV-2 vaccine administration.

These recommendations may be subject to change based on the evolving knowledge around the use of SARS-CoV-2 vaccines in patients with HCV and as more data are collected in real-world scenarios and clinical trials.

Any SARS-CoV-2 vaccine information must be documented on the COVID-19 vaccine electronic Case Report Form (eCRF). Refer to the Operations Manual for instructions on reporting any AEs associated with the COVID-19 vaccine.

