5.6 Follow-Up After Subject Discontinuation of Study Drug or from Study

To minimize missing data for efficacy and safety assessments, subjects who prematurely discontinue study drug treatment should continue to be followed for all regularly scheduled visits, unless subjects have decided to discontinue the study participation entirely (withdrawal of informed consent). Subjects should be advised on the continued scientific importance of their data even if they discontinue treatment with study drug early.

If a subject prematurely discontinues study participation (withdrawal of informed consent), the procedures outlined for the Premature Discontinuation visit should be completed as soon as possible, preferably within 2 weeks. In addition, if subject is willing, a 30-day follow-up phone call after the last dose of study drug may be completed to ensure all treatment-emergent AEs/SAEs have been resolved.

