7.2 Definition for Analysis Populations

The ITT population is defined as all enrolled subjects who received at least 1 dose of study drug. The ITT population will be used for the primary efficacy analysis and other secondary efficacy analyses.

The mITT-VF population is defined as all enrolled subjects who received at least 1 dose of study drug, excluding those who did not achieve SVR₁₂ for reasons other than virologic failure (i.e., those with HCV reinfection, those who did not achieve SVR₁₂ due to early premature discontinuation of study drug, and those who were missing HCV RNA data in the SVR₁₂ window after backward imputation). The mITT-VF population will be used for the key secondary efficacy analysis.

The Safety Analysis Set consists of all subjects who received at least 1 dose of study drug.

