APPENDIX D. ACTIVITY SCHEDULE

The following table shows the required activities for this study. The individual activities are described in detail in the **Operations Manual**. Allowed modifications due to COVID-19 are detailed in the Operations Manual.

Study Activities Table

Activity	Screening (Day –30 to Day –1)	Baseline (Day 1)	Week 2	Week 4	Week 8 (EOT) or Premature D/C from Treatment	PT Week 4	PT Week 12 or PT Premature D/C
Informed consent	✓						
Eligibility criteria	· ·	✓					
Medical/surgical history (update on Day 1)	· ·	· ·					
Alcohol and nicotine use	· ·						
Adverse event assessment	· ·	✓	1	✓	1	1	 Image: A second s
Prior/concomitant therapy	· ·	•	· ·	· ·	· ·	· ·	· ·
		· ·			•		· ·
Patient Reported Outcomes (EQ-5D-5L, FSS) Questions on hepatitis C risk behaviors	✓				· · · ·		
Questions on experience with opioid substitutes and non-prescribed illicit drug use		~			×		×
* EXAMS							
12-lead ECG	 Image: A second s						
Height (screening only) and weight	 ✓ 	 Image: A second s	✓	 Image: A second s	✓	✓	✓
Vital signs	×	×	✓	×	×	×	 Image: A second s
Physical examination	~	 Image: A second s			✓		✓
Child-Pugh score (cirrhotic subjects and subjects with indeterminate cirrhosis status only)	~	×			✓		
Hepatic decompensation assessment	×	√					
HCC screen by ultrasound, if cirrhotic or indeterminate cirrhosis status	~						
Second Labs			I				
SARS-CoV-2 testing (e.g., PCR)	×						
Review of signs/symptoms of SARS-CoV-2 infection at Day 1, then as suspected		×					

Activity	Screening (Day –30 to Day –1)	Baseline (Day 1)	Week 2	Week 4	Week 8 (EOT) or Premature D/C from Treatment	PT Week 4	PT Week 12 or PT Premature D/C
CENTRAL LABS							
HIV-1 RNA (only for HCV/HIV coinfected subjects)	✓	 Image: A second s	<	 Image: A second s	✓	 Image: A second s	✓
Anti-HCV antibody, HIV antibody, and HBsAg	✓						
Hematology, clinical chemistry, urinalysis, coagulation panel	✓	×	✓	×	*	×	×
Pregnancy test (for female confirmed to have child- bearing potential [S-serum; U-urine])	√(s)	√(u)		√(u)	√(u)	√(u)	√(u)
FSH (female with no menses for > 12 months)	×						
HCV genotype/subtype	×						
Hepatitis B Panel	×						
HbA1c	×						
Total Insulin		×					1
Fibrotest and APRI (or Fibroscan or Liver Biopsy)	×						
HCV RNA	✓	×	✓	 Image: A second s	✓	×	×
HCV resistance sample		×	×	 Image: A second s	×	×	 Image: A second s
Archive sample	×	×	✓	 Image: A second s	×	×	×
Drug/Alcohol Screen	×						
Flow cytometry CD4+ (only for HCV/HIV coinfected subjects)	*						

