    - yes, started prior to start of study treatment with last dose less than 6 months prior to start of study treatment (Recent);
    - yes, started prior to start of study treatment with last dose 6 to 12 months prior to start of study treatment (Recent);
    - yes, started during study treatment period (Current).
  - Former/Non-PWID defined with non-prescribed illicit injection drug use as:
    - yes, started prior to start of study treatment with last dose more than 12 months prior to start of study treatment (Former);

- yes, started prior to start of study treatment and timing of last dose unknown (Former);
- yes, started after last dose of study treatment (Non-PWID);
- no (Non-PWID).
- PWID Status Classification 3 PWID classification defined with respect to study participation (current/recent PWID or former/non-PWID; current PWID, recent PWID, former PWID, or non-PWID)
  - Current/Recent PWID defined with non-prescribed illicit injection drug use as:
    - yes, started prior to start of study treatment and ongoing as of end of study participation (Current);
    - yes, started prior to start of study treatment with last dose after last dose of study treatment (Current);
    - yes, started prior to start of study treatment with last dose during study treatment period (Current);
    - yes, started prior to start of study treatment with last dose less than 6 months prior to start of study treatment (Recent);
    - yes, started prior to start of study treatment with last dose 6 to 12 months prior to start of study treatment (Recent);
    - yes, started during study treatment period (Current);
    - yes, started after last dose of study treatment (Current).
  - Former/Non-PWID defined with non-prescribed illicit injection drug use as:
    - yes, started prior to start of study treatment with last dose more than 12 months prior to start of study treatment (Former);
    - yes, started prior to start of study treatment and timing of last dose unknown (Former);
    - no (Non-PWID).

- History of opiate substitution therapy use (yes, ongoing at start of study treatment; yes, less than 6 months prior to start of study treatment; yes, 6 to 12 months prior to start of study treatment; yes, more than 12 months prior to start of study treatment; yes, timing of last dose unknown; or no);

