## 9.2 Handling of Missing Data

### **Missing Data Imputation for SVR**

For analyses of SVR, subjects missing visit values will have backward imputation applied, if possible. For backward imputation, if the nearest HCV RNA value after the SVR window is unquantifiable or undetectable, then it will be used to impute the HCV RNA value in the SVR window. If a subject is missing an HCV RNA value within the appropriate SVR window after performing backward imputation, then this value will be imputed with an HCV RNA value from a local laboratory if present; otherwise, the HCV RNA value will be missing. A subject with missing HCV RNA data in the analysis window, after imputations, will be imputed as a failure.

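### The ITT SVR12 rows for timing of illicit drug use depend on how long a subject is followed, so loss to follow-up affects both the row and the result

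*SAP*

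**What the plan says.** SAP 9.6 presents SVR12, in the ITT and mITT-VF populations, by history of illicit drug use and of illicit injection drug use. The rows begin "yes, ongoing as of the end of study participation; yes, last dose after last dose of study treatment". They continue with last use during treatment, bands of time before treatment, timing unknown, and none. Use must have started before study treatment, but that fixes only when use began; the last dose decides the row. SAP 7.1 places the same variables among the categorical baseline characteristics.

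PWID Status Classification 1 in SAP 7.1 is labelled as relative to the start of study treatment. Its Current level nevertheless consists of injecting recorded during or after treatment, or still ongoing at the end of participation. Last use in the 12 months before Day 1 is Recent.

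On missing outcomes, SAP 9.2 states: "A subject with missing HCV RNA data in the analysis window, after imputations, will be imputed as a failure". The mITT-VF population instead leaves out "those who were missing HCV RNA data in the SVR₁₂ window after backward imputation" (Protocol 7.2).

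On data collection, Protocol 5.4 says: "Nonprescribed illicit drug use must be recorded throughout the study". In Protocol Appendix D, the row "Questions on experience with opioid substitutes and non-prescribed illicit drug use" appears to be ticked at Baseline, Week 8 and PT Week 12, as far as the extracted table can be read. Prior and concomitant therapy is also ticked at PT Week 4.

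The same subgroup list handles another drug-use variable differently: "History of opiate substitution therapy use (yes, ongoing at start of study treatment; yes, less than 6 months prior to start of study treatment". That variable is anchored at the start of study treatment. Neither document sets a landmark for the illicit-use rows or cautions the reader about them.

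**The concern.** A row that needs observation after treatment can hold only subjects who were seen after treatment. Someone who disappears on treatment cannot be recorded as last using after it. That person is placed in another row and, having no HCV RNA in the SVR12 window, normally counts as an ITT failure. Retention thus influences the row and the outcome together.

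The four-level Classification 1 has a related problem. An active injector lost soon after Day 1, with no later use recorded, can be coded Recent rather than Current and also be a failure.

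The documents do not say that these rows are meant to answer whether continued use impairs cure; the rationale in SAP 13.1 is alignment with data collection and several definitions of PWID status. But the protocol describes PWID as the most prevalent group in acute HCV and admits current injectors, so readers are likely to use the rows that way. The Wilson intervals attached to subgroups of 5 or more do not reflect this bias.

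**Working it through.** **The plan's own figures.** The plan gives no figure for these subgroup rates. Its power statement for the primary endpoint (80%, 283 subjects, 88.7% against 82.7%) reproduces: the Wilson rule needs 247/283 and has exact power 80.4%. It is not in dispute. For a scale of loss, the historical PWID data (Protocol 4.2) give 55/62 = 88.7% SVR12 and 1/62 virologic failure. That leaves 62 - 55 - 1 = 6 other failures, 6/62 = 9.7%. The sample-size section assumes about 10% outside mITT-VF (283 x 0.9 = 254.7, stated as 255). Both figures count all non-virologic failures, so 10% is an upper case for loss before any post-treatment contact.

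**Assumptions, none from the documents.**
- Cure is 98% in everyone seen and unrelated to drug use.
- A share L is lost, unrelated to drug use, with no post-treatment contact; all of these are ITT failures.
- True last use among Day 1 injectors (before / during / after / ongoing) is 20/15/30/35% (pattern A) or 30/30/20/20% (pattern B).
- Lost subjects whose last use was before treatment keep their row. The other lost subjects are split between during and ongoing in proportion to the size of those rows.

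**Formula.** Row rate = 0.98 x seen / (seen + lost assigned to the row). The true ITT rate in every row is 0.98 x (1 - L): 88.2% at L = 10% and 93.1% at L = 5%.

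**L = 10%, per 100 injectors.**
- Pattern A: 1.5 + 3.0 + 3.5 = 8.0 lost subjects to place; 2.4 go to during and 5.6 to ongoing. During: 13.5 x 0.98 / (13.5 + 2.4) = 13.23/15.9 = 83.2%. Ongoing: 31.5 x 0.98 / (31.5 + 5.6) = 30.87/37.1 = 83.2%.
- Pattern B: 7.0 to place; 4.2 go to during and 2.8 to ongoing. During: 26.46/31.2 = 84.8%. Ongoing: 17.64/20.8 = 84.8%.
- After-treatment row, either pattern: 98.0%. This is a ceiling, because no lost subject can enter it here.

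**L = 5%.**
- Pattern A: 4.0 to place. During: 14.25 x 0.98 / (14.25 + 1.2) = 90.4%; ongoing is the same.
- Pattern B: 3.5 to place. During: 28.5 x 0.98 / (28.5 + 2.1) = 91.3%; ongoing is the same.

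**Sensitivity to coding and contact.**
- All placed in one row: at L = 10%, pattern A with ongoing gives 30.87/39.5 = 78.2% and with during gives 13.23/21.5 = 61.5%; pattern B gives 17.64/25 = 70.6% and 26.46/34 = 77.8%. At L = 5% the range is 76.5-87.5%.
- Half of the lost seen once after treatment and kept in their true row, L = 10%, pattern A: after = 26.46/(27 + 1.5) = 92.8%; during = 13.23/(13.5 + 0.75 + 1.2) = 85.6%. Pattern B gives 92.8% and 26.46/(27 + 1.5 + 2.1) = 86.5%. The gap is about 6-7 points.

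**Low loss, a second model.** Fix overall SVR12 at S = 88.7% and let a share q = 10-50% truly have last use after treatment. The after row is S/(1 - L); all other rows pooled are (1 - q)S/(1 - q(1 - L)). At L = 2% this gives 90.5% against 88.5% to 87.0%, a gap of 2.0-3.5 points. At L = 5% the gap is 5.2-8.9 points.

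**The case against.** Much of the case on the other side stands.

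- The plan shows every SVR12 subgroup in mITT-VF as well, where subjects missing SVR12 data are excluded. The mechanism largely disappears there. The plan also tabulates and lists reasons for non-response, so missing data can be told apart from virologic failure.
- The after-treatment row is not free of failures. It needs some contact after the last study dose, not an SVR12 visit. Protocol 5.6 also says that "subjects who prematurely discontinue study drug treatment should continue to be followed for all regularly scheduled visits". Someone seen at PT Week 4 and then lost can be in this row and fail, so 98% is a ceiling.
- Chance variation is of similar size. Even if all 283 subjects were injectors, an after-treatment row of 20-30% holds about 57-85 subjects. At 92.8%, 1.96 x sqrt(0.928 x 0.072 / n) is 6.7 to 5.5 points.

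Three stronger readings are tempting, and the documents do not support them.

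- A reader might infer very large distortions, with rows near 60-78%. These need every lost subject outside the pre-treatment row to be coded to a single row. The documents state no such convention.
- A reader might infer that the primary threshold is biased. For use begun before treatment, the ongoing, after and during rows are all Current in Classification 1, and a move from Current to Recent stays on the current/recent side. A move to Former would need something else, such as last use coded as of unknown date; the documents do not say that lost subjects are coded that way.
- A reader might extend the point to the virologic-failure and reinfection tables by Classifications 2 and 3. Those endpoints have no rule that counts missing data as failure, so this mechanism does not carry over.

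None of this removes the dependence of the ITT rows on follow-up, which follows from the definitions themselves.

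**Conclusion.** The point holds for the ITT SVR12 tables by illicit drug use and illicit injection use, and in related form for the four-level Classification 1. Their rows mix drug-use history with length of follow-up, and follow-up also drives the ITT outcome. Under a proportional split, the ongoing and during rows are understated by about 3-5 points at 10% loss (83.2-84.8% against 88.2%) and about 2-3 points at 5% loss (90.4-91.3% against 93.1%). The after-treatment row is overstated by at most 9.8 and 4.9 points respectively. These sizes depend on assumed loss, patterns of use and coding. The tables are descriptive, so type I error and the primary conclusion are unaffected. This is an inexpensive improvement to how subgroup results can be read.

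**What to change.** In SAP 7.1 and 9.6, define the ITT SVR12 subgroups for illicit drug use and illicit injection use, and the four-level Classification 1 rows, from status at Day 1: ongoing at the start of study treatment, under 6 months, 6-12 months, over 12 months, timing unknown, none. This is the scheme already used for opiate substitution therapy, and the Baseline questions supply the data.

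Present SVR12 by use during or after treatment, and by Classifications 2 and 3, only among subjects with drug-use data through PT Week 12. Label those tables as conditional on follow-up.

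Leave the two-level current/recent definition that feeds the efficacy thresholds (SAP 9.3.2 and 9.4.2) as written. Footnote any subject whose Day 1 row disagrees with it, for example someone whose injecting lapsed more than 12 months before Day 1 and resumed on study.

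The cost is SAP wording, reprogramming of the subgroup tables, and fewer subjects in the later-use tables. No new data collection is needed.
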